11.6. Randomization

Randomization will occur after all clinical and transthoracic echo criteria have been verified and the baseline assessment is complete. Randomization will occur no later than 30 days following consent. Subjects will be randomized 1:1 (Device: Control) and randomization will be stratified by sequential vs. concomitant planned ablation to help ensure balance of treatment assignments within the sequential and concomitant groups.

11.6.1. Sequential Ablation group

Randomization must occur between 90 and 180 days after the most recent AF ablation procedure. If the subject is randomized to the device group, implant must occur within 10 days of randomization.

For roll-in subjects, the implant must occur between 90 and 190 days after the most recent AF ablation.

11.6.2. Concomitant Ablation group

Randomization must occur within 10 days prior to the planned ablation. If the subject is randomized to the device group, catheter ablation and device implant must occur within 10 days of randomization.

11.7. Index Procedure

For all patients undergoing ablation and/or WATCHMAN FLX implantation, the following data will be collected:

 Physical assessment including vital signs, weight, and rhythm at time of the procedure

- Current medication regimen review for the use of antiplatelet, NSAID, anticoagulant, and antiarrhythmic medications
- Ablation information (patients undergoing Ablation) including ablation type, success, and rhythm post-ablation
- Adverse events experienced at index procedure and since enrollment. Refer to Section 21 for detailed information on Safety reporting
- Discharge information (date, time)

For patients undergoing WATCHMAN FLX implantation, the procedure should be performed using standard of care methods established by the investigational site (e.g., sterile technique, personnel requirements, etc.). Implantation of the WATCHMAN FLX Device shall only be performed by study physicians trained in percutaneous and transseptal procedures who have completed the WATCHMAN and/or WATCHMAN FLX physician training programs. Refer to the WATCHMAN FLX Instructions for Use (IFU) for detailed instructions regarding the implantation and use of the WATCHMAN FLX Device.

Notes:

- 1. TEE is recommended for implant procedures; however, intracardiac echocardiography (ICE) is an acceptable alternative and may be used if the following conditions are met:
 - Pre-planning LAA imaging using TEE or CT must be completed prior to the implant procedure.
 - The implanting physician must have performed ≥ 25 WATCHMAN and/or WATCHMAN FLX procedures that involve the use of ICE.
 - If ICE is used, the site must perform pre-planning LAA imaging and must specify in the eCRF what imaging modality was used.
- 2. Do not proceed with the WATCHMAN FLX implant if the following is observed on TEE/ICE or fluoroscopy:
 - Intracardiac thrombus, LAA sludge (gelatinous, non-adherent, intracavitary echodensity more layered than dense spontaneous echo contrast (SEC) seen continuously throughout cardiac cycle) or dense SEC.
 - Complex atheroma with mobile plaque of the descending aorta and/or aortic arch.
 - The LAA anatomy will not accommodate a WATCHMAN FLX closure device.
 - High-risk PFO not detected at baseline.

Additional data collected for patients undergoing WATCHMAN FLX implantation:

- WATCHMAN FLX Device usage information, including device size and compression post-implant (Device Group only);
- Access System(s) usage information
- LAA imaging (as described in **Section 11.10**): LAA size/shape, number of lobes in LAA, and location of lobes to ostium;
- Device Release Criteria
- Name of implanting physician

- Duration of procedure and fluoroscopy
- Procedural medications
- Type of anesthesia
- Device Deficiencies
- Discharge information (date, time)

11.8. Study Medication Regimen

11.8.1. Device Group Study Medication Regimen

After the WATCHMAN FLX implant, Device Group subjects will be prescribed market-approved OAC and aspirin (75-100mg recommended) until the 3-month visit followed by aspirin until at least the 12-month visit (recommended for duration of the trial).

Any changes to protocol required medications or antiarrhythmic medications must be captured in the appropriate medication log.

11.8.2. Control Group Study Medication Regimen

Following randomization, control subjects must continue or start market approved OAC used per IFU for atrial fibrillation stroke prevention and should remain on it for the duration of the trial.

11.9. Follow-Up Procedures (Office(preferred) or Phone call)

Subjects will be followed at office visits (preferred) or phone visit at 3 months (90 ± 15 days from randomization), 12 months (365 ± 30 days from randomization), 24 months (730 ± 60 days from randomization), and 36 months (1095 + 60 days from randomization - visit must occur on or after day 1095).

Data from a physical assessment that is performed at an outside facility/non study trained personnel as part of the patient standard of care, may be utilized for the purpose of a protocol-required subject visit if completed within the follow up visit window. These data are to be reviewed by an investigator on the delegation log for inclusion of data as part of the study. Any other data that is collected from an outside facility as part of the standard of care (such as imaging) of the patient may be considered for inclusion as part of the study data.

Note: for Roll-in subjects the date of implant will be used to calculate Follow-up windows instead of the date of randomization.

The following will be assessed during each visit and documented on case report forms:

- Re-do ablations
- Documented atrial fibrillation episode since prior visit
- New onset atrial flutter or atrial tachycardia event (≥ 30 seconds in duration or from a 10 second 12-lead EKG; electrical and/or pharmacological cardioversion for AFL/AT)

- LAA imaging (as described in **Section 11.10**) for all Implant patients (submitted to core lab). LAA imaging data will include:
 - o Device position
 - o LAA seal status
 - o Thrombus on the device surface (if visualized)
 - o Intracardiac thrombus (if visualized)
 - Residual atrial septal shunt (if visualized)
- *Note LAA imaging must be performed at 3-months and 12-months follow-up. If
 performed at the later visits or at the time of an adverse event, the information will be
 collected in the database. Intent and Attempt patients will not have 3-month or 12month LAA imaging performed. Physical assessment including vital signs, weight, and
 rhythm at time of the visit.
- Modified Rankin Scale (MRS) and National Institutes of Health Stroke Scale (NIHSS). Note: NIHSS may not be performed remotely as part of a phone visit follow-up.
- Current medication regimen for the use of antiplatelet, NSAID, anticoagulant, and antiarrhythmic medications. Dose changes, medication interruptions, and medication cessation must be documented
- Quality of Life Questionnaires at 12-month and 36-months. Note: phone interview script will be available for use.
- Adverse events since previous visit. Refer to **Section 21** for detailed information on Safety reporting
- Device Deficiencies

11.10. LAA Imaging (TEE, ICE, and CT)

Roll-In and Device Group subjects may undergo pre-planning LAA imaging (typically TEE or CT) prior to WATCHMAN FLX Device implant. Pre-planning LAA imaging is not required for subjects undergoing TEE guided implants. If pre-planning imaging is performed, sites must note this on the data collection form and the imaging study should be saved and made available to the sponsor upon request. Pre-planning LAA imaging is required for subjects undergoing ICE guided implants and must be performed according to the imaging manual and sent to the Core Lab.

11.10.1. Baseline Transthoracic Echocardiogram (TTE)

The baseline TTE will be done to evaluate all exclusion criteria and to confirm subject eligibility. Criteria obtained from a cardiac imaging performed within 180 days prior to randomization may be used if all the exclusion criteria can be evaluated. If all exclusion criteria were not obtained on the prior cardiac imaging, a TTE will have to be conducted at baseline. If a significant cardiac event occurs after the cardiac imaging which causes a change in cardiac status [i.e., major Congestive Heart Failure (CHF) decompensation] the baseline TTE must be repeated after informed consent and prior to randomization.

If a subject meet any of the echo exclusion criteria, they should be screen failed and withdrawn immediately.

11.10.2.Implant and Follow-Up Imaging (TEE/ICE/CT)

All protocol required LAA imaging will be performed in accordance with the Core Lab Imaging Manual.

Implant LAA imaging (TEE recommended) will allow the investigator to obtain proper measurements of the LAA to correctly size the device, confirm device release criteria are met prior to device release, document absence of intracardiac thrombus, and confirm adverse events have not occurred during the implant procedure (i.e., pericardial effusion).

TEE is recommended for implant procedures; however, ICE may be used by investigators that meet the following conditions:

- Pre-planning with TEE or CT must be performed prior
- The implanting physician has performed ≥ 25 WATCHMAN and/or WATCHMAN FLX procedures that involve the use of ICE

The 3-month and 12-month LAA imaging (TEE recommended) is conducted to assess flow through and around the WATCHMAN FLX Device and to verify there is no device related thrombus (DRT) on the surface of the device. Adequate LAA seal is defined as demonstration of peri-device flow ≤5 mm around the margins of the WATCHMAN FLX Device.

Copies of all protocol required LAA imaging must be provided to the core lab per the Imaging Manual. LAA Imaging must be saved and available for review in the subject's medical or study file. Certain information from the LAA imaging conducted during the course of the study, including any non-protocol required LAA imaging (such as that performed in the context of an embolic event; see **Section 11.11.2**), will be captured on the study case report forms and submitted to the core lab. All study required images must be identified as defined in the Imaging Manual.

11.11. Stroke or Systemic Embolism

In the event that a subject experiences a stroke or systemic embolism (SE) during the course of the study, supporting documentation will be requested by the sponsor in an attempt to search for causes of stroke or embolic event.

11.11.1.Stroke Scales

The National Institutes of Health Stroke Scale (NIHSS) is an assessment tool which quantifies stroke-related neurological deficit. It must be conducted by neurologist or personnel who have a current certification to conduct the NIHSS. It is routinely collected at Baseline and all **office** Follow-up visits for all subjects and should be collected at the time of stroke or TIA event. If administered at the time of event, the NIHSS may be obtained by non-study personnel. The Modified Rankin Scale (MRS) score assesses the severity of stroke disability and functional dependence of all subjects. The assessment must be

Confidential Form/Template 90702637_Rev/Ver AP OPTION Protocol, document # 92320955, Rev E Page 55 of 102

performed by either a neurologist or personnel who have completed a certification for the MRS. The MRS to be collected at Baseline and Follow-up visits (office or phone) for all subjects. It must also be collected following the stroke or TIA event and at 90 (+/- 15) days after a stroke or TIA event. The MRS collected following the stroke or TIA event, and at 90 (+/- 15) days after a stroke or TIA event may be obtained by non-study personnel.

Note: The person administering the stroke scales should be blinded to the subject's treatment assignment.

Note: Neurologic consultation and cerebral vascular imaging should be performed if a subject's NIHSS and MRS have worsened and/or if there is suspicion of a neurologic event. If neurologic consultation and/or cerebral vascular imaging does occur, BSC may request a copy.

11.11.2. Stroke or Systemic Embolism and LAA Imaging (All subjects)

LAA imaging is strongly encouraged to help better ascertain the mechanism of the stroke or SE. This is not required, however if collected the imaging study should be saved and sent to the core lab per Imaging Manual. An optimal evaluation includes, where feasible based on subject status and technical considerations, evaluation of:

- LA thrombus size, location, mobility, etc.
- Agitated saline contrast injection to evaluate presence of residual right to left shunt at the atrial level (persistence of PFO or residual puncture hole from transseptal catheterization for device placement)
- Presence, location, and grade of ascending and arch aortic atheroma
- Presence of worsening left ventricular dysfunction, "new" regional wall motion abnormality or presence of LV thrombus
- If applicable:
 - WATCHMAN FLX Device seal or presence (and measurement) of peri-device flow
 - WATCHMAN FLX Device thrombus or pannus size, location, mobility, etc.

11.12. Device Thrombus

The most accurate determination of whether thrombus has formed on the surface of the WATCHMAN Device is through TEE evaluation. In the case of thrombus on the atrial facing side of the device, anticoagulation therapy should be initiated per hospital standard of care, for treatment of thrombus. After the course of anticoagulation therapy, a repeat imaging evaluation should be performed to confirm the thrombus has resolved. This is not required, however if collected the image should be saved and sent to the core lab per Imaging Manual. Cessation of anticoagulation after this timepoint is at the discretion of the investigator.

Confidential Form/Template 90702637_Rev/Ver AP OPTION Protocol, document # 92320955, Rev E Page 56 of 102

Any identification of device thrombus must be reported on an adverse event CRF. A copy of all imaging conducted for evaluation of potential thrombus must be sent to the Echo Core Lab and a copy must be maintained in the subject's records at the site.

TEE is recommended for follow-up imaging, but CT is an acceptable alternative. However, if findings suspicious for significant DRT (hypoattenuated thickening \geq 3mm) or any pedunculated thrombus is noted on CT at follow-up, a TEE must be performed to determine if therapy is required.

11.13. Device Seal

For those subjects receiving a WATHCMAN FLX device, if adequate device seal (i.e., no leak > 5mm) is not obtained as demonstrated by the 3-month post-implant imaging (TEE or CT), the decision to continue or stop OAC and/or aspirin is at the discretion of the investigator and should be based on the individual subject's risk/benefit analysis (if possible, OAC should generally be prescribed). Follow-up imaging may be performed prior to the 12-month visit to reassess seal and inform the decision to stop OAC and/or aspirin. If device seal is not obtained as demonstrated by the interim or the 12-month imaging (TEE or CT), the decision to continue or stop OAC and/or aspirin is at the discretion of the investigator (if possible, OAC should generally be prescribed).

Note: Clinical study data establishing safety and effectiveness are based on demonstration of peri-device flow ≤5 mm as a measure of adequacy of LAA seal. Per the WATCHMAN FLX IFU, if adequate seal is not demonstrated, decision to discontinue OAC is at physician discretion provided that any leak demonstrated is ≤ 5 mm. Non-approved measures/procedures to improve seal (e.g. 'kissing' WATCHMAN, vascular plugs, endovascular coils, etc.) must not be attempted during the course of this study.

TEE is recommended for follow-up imaging, but CT is an acceptable alternative. However, if findings suspicious for significant peri-device leak (PDL) (e.g. leak width > 3mm) is noted on CT at follow-up, a TEE must be performed to determine if therapy is required.

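### Protocol 11.13 contradicts itself on stopping OAC when the peri-device leak exceeds 5 mm: a low-priority subject-safety correction, unlikely to affect non-inferiority materially

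*Protocol*

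**What the plan says.** The body of Protocol 11.13 defines adequate seal as no leak above 5 mm. If 3-month imaging does not show it, "the decision to continue or stop OAC and/or aspirin is at the discretion of the investigator and should be based" on the individual risk and benefit. The same discretion is given again at interim or 12-month imaging. Both times a preference is added in parentheses: "if possible, OAC should generally be prescribed".

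The Note that follows says that the supporting safety and effectiveness data rest on flow of 5 mm or less. It then reports the instructions for use (IFU): if adequate seal is not shown, the "decision to discontinue OAC is at physician discretion provided that any leak demonstrated is" 5 mm or less.

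Three other places bear on the rule:

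- Section 11.10.2 uses the same threshold: "Adequate LAA seal is defined as demonstration of peri-device flow" of 5 mm or less.
- Section 11.8.1 prescribes OAC and aspirin "until the 3-month visit followed by aspirin until at least the 12-month visit", with no seal condition.
- Section 20.4 says that Device subjects may stop anticoagulation from the 3-month visit if they meet guidelines for stopping it. It does not say what those guidelines are.

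**The concern.** For a leak above 5 mm, the body lets the investigator stop OAC. The Note, as it reports the IFU, gives no such discretion. Section 18.2 requires the device to be used in accordance with both the protocol and the directions for use, so a site that relies on the body could depart from the IFU as the Note describes it.

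The subject at risk is one whose appendage is not adequately sealed and whose anticoagulant is withdrawn. Section 20.4 itself names the absence of an anticoagulant as a possible risk if the device is not effective. Under section 15.3 the core laboratory is not a reference for subject management, so the site decides alone.

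Any extra strokes would count in the Device arm's primary efficacy endpoint, so the effect on the non-inferiority test also has to be sized.

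**Working it through.** **The texts side by side**

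| Leak on imaging | Body of 11.13 | Note in 11.13 (reporting the IFU) |
|---|---|---|
| Above 5 mm | Stop or continue at discretion; OAC preferred | No discretion to stop |
| 5 mm or less | Seal adequate; body rule not triggered | Discretion to stop |

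The texts diverge only when OAC is stopped with a leak above 5 mm. The Note's own condition is also nearly empty. With adequate seal defined as 5 mm or less, a measured leak can hardly be both inadequate and within 5 mm. If adequate is read instead as complete seal, the Note makes sense, but its limit of 5 mm then conflicts with the body more plainly.

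**The plan's own figures**

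The documents give no number for this rule. The figure it could touch is the power of the primary efficacy test. With 680 per arm, 10% in both arms, a 5-point margin and one-sided alpha of 0.025, the Farrington-Manning calculation gives 85.88% (stated: 85.9%). An analytic Greenwood calculation with 800 per arm and 15% attrition gives 89.2% (SAP simulation: 89.3%).

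**How many subjects**

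Protocol 4.2 reports closure with flow of 5 mm or less at 12 months in an earlier single-arm study of this device: 100%, with a one-sided 95% lower bound of 99.1%. Leaks above 5 mm are therefore 0, with an upper bound of 1 − 0.991 = 0.9%.

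- All 800 Device subjects: 800 × 0.009 = 7.2.
- If 98.5% are implanted (registry figure in 4.2): 788 × 0.009 = 7.1.
- After 15% attrition: 680 × 0.009 = 6.1.

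**Excess strokes if all 7.2 stop OAC at month 3**

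Time at risk is 36 − 3 = 33 months, or 2.75 years. Rates per 100 patient-years:

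- Off OAC, low: 5 (Protocol 4.1, average ischemic stroke rate in non-valvular AF, not stated to be off therapy).
- Off OAC, high: 7.2 (Protocol 4.2, calculated rate without preventive therapy in the European registry).
- On OAC: 0.73 (Protocol 4.2, control arm of the second pivotal study).

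Excess = 7.2 × [(1 − exp(−r × 2.75)) − (1 − exp(−0.0073 × 2.75))], where r is the off-OAC rate per year.

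- r = 0.05: 7.2 × (0.1285 − 0.0199) = 0.78 strokes; 0.78/800 = 0.10 points; 0.10/5 = 2.0% of the margin.
- r = 0.072: 7.2 × (0.1796 − 0.0199) = 1.15 strokes; 1.15/800 = 0.14 points; 0.144/5 = 2.9% of the margin.

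**Effect on the test**

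Without subtracting the on-OAC rate, 0.9% × 18% = 0.16 points. Power of the Kaplan-Meier test then falls from 89.2% to 86.9%.

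If OAC is continued instead, intention-to-treat analysis keeps these subjects in the Device arm on the control therapy. Suppose they behave like controls and the true difference among the rest is exactly 5 points. Type I error then rises from 2.50% to 2.66% at a leak rate of 0.9%.

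For illustration only, since no document supports such rates: if OAC is stopped, leak rates of 2% and 5% would add 0.36 and 0.90 points and lower power to 83.7% and 72.9%.

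**The case against.** The strongest reply is that safeguards already exist. The preference for OAC is stated twice. An investigator who continues OAC satisfies both texts, so a careful site reading the whole section would follow the stricter one. Section 20.4 makes stopping conditional. A CT that suggests a significant leak must be followed by TEE. Stops are recorded: "Any changes to protocol required medications or antiarrhythmic medications must be captured in the appropriate medication log", and at follow-up visits "Dose changes, medication interruptions, and medication cessation must be documented". Eligibility already requires suitability for OAC. The conflict is also with a one-sentence report of an IFU that is not among the documents.

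Most of this stands, and it is why the point ranks low. It does not remove the contradiction. The preference is not binding, the condition in 20.4 is undefined, and neither recording requirement asks why OAC was stopped. The limit on the evidence is accepted: the finding rests on what the Note reports, and no departure from the actual IFU is shown.

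A reader might infer that the two rules can never be followed together, or that the inconsistency undermines the non-inferiority conclusion. The documents support neither. Continuing OAC meets both rules, and at the documented leak rate the shift is a small fraction of the margin. The opposite inference, that non-inferiority is certainly unaffected, is not supported either. The leak figure is from month 12 in another population, while the rule first acts at month 3 in subjects who have had ablation.

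**Conclusion.** The inconsistency is real. The body of 11.13 allows OAC to be stopped with a leak above 5 mm, the Note in the same section does not, and neither 11.8.1 nor 20.4 resolves it. It is a wrong rule for a safety decision, of low priority because few subjects should meet it.

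The expected size is 0 to about 7 of 800 Device subjects, with a point estimate of 0. If every one of them stopped OAC at month 3, against the stated preference, the excess is about 0.8 to 1.15 strokes, or 0.10 to 0.14 points against the 5-point margin. A material effect on non-inferiority is unlikely at that leak rate but not excluded.

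This rests on three assumptions: that the 12-month bound of 0.9% carries over to month 3 and to OPTION subjects, that 5 to 7.2 strokes per 100 patient-years represents risk off OAC with an inadequate seal, and that event times are exponential. The 7.2 comes from a registry with a mean CHA2DS2-VASc score of 4.5, where about 72% were judged unsuitable for OAC. OPTION admits men from a score of 2 and women from 3, all suitable for OAC.

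**What to change.** Change the body text of 11.13 only. For 3-month, interim and 12-month imaging, state that:

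- OAC is continued while a leak above 5 mm persists, unless contraindicated;
- the reason for any stop is recorded;
- discretion to stop applies only to residual flow of 5 mm or less.

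Leave the Note's report of the IFU as it is unless it is checked against the IFU itself, because rewording it unseen could misreport the source.

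The cost is a short amendment, which needs IRB/EC/REB review and approval under 18.3, and a letter to sites. Investigators lose a little discretion for leaks above 5 mm. Sample size, stated power and planned analyses do not change.
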